7.6.1.5 Other Adverse Events

- Mucositis: Significant mucositis from radiation and cisplatin is expected and will not be an indication for cisplatin dose modification. No cisplatin dose reductions will be made.

- Ototoxicity: For new clinical hearing loss not requiring a hearing aid or for tinnitus that interferes with activities of daily living, treat at 50% dose reduction. For hearing loss requiring a hearing aid, discontinue cisplatin. Continue RT and lapatinib/placebo.
- If the physician is unsure about the severity of the hearing loss, an audiogram is encouraged.

7.6.1.6 If the second dose of cisplatin is delayed more than 21 days because of hematologic or renal adverse events, that dose will be omitted.

7.6.2 Lapatinib/Placebo Modifications

Patients will be treated per protocol as described in Section 7.2.2 or until disease progression or withdrawal from treatment due to unacceptable adverse event or treatment consent withdrawal.

If lapatinib dose reduction is required the following general rules should be applied:

- Lapatinib/placebo dose should be reduced by increments of 250 mg at a time and only after all supportive care measures have been exhausted without an improvement of patient status.
- Lapatinib/placebo should not be used at doses below 1000 mg if given as monotherapy or below 750 mg concomitantly with cisplatin.

See the table below for a summary of dose holding/interruptions and dose de-escalation recommendations in case of lapatinib-related adverse events (graded according to CTCAE, v. 4). See Section 7.7 below for management guidelines of lapatinib adverse events.

Adverse Event (CTCAE, v. 4)	Action
Non-hematological, grade 1 or 2 (Not attributable to cisplatin or radiation)	Continue lapatinib therapy at full dose prescribed. Apply maximum supportive care recommendations. If prolonged duration of grade 2 adverse event is affecting quality of life a one-time decrease of dose by 250 mg is allowed.
Non-hematological, grade 3 or 4 (Not attributable to cisplatin or radiation)	
Apply maximum supportive care recommendations. Hold lapatinib therapy until recovery to grade ≤ 1 (up to 14 days).
 
In patients with symptomatic grade 3 or 4 left ventricular cardiac dysfunction, lapatinib must be permanently discontinued. For grade 3 or 4 interstitial pneumonitis or grade 4 rash manifested as toxic epidermal necrolysis (e.g. Stevens-Johnson Syndrome etc.), lapatinib must be permanently discontinued.
 
If recurrence of adverse event after drug hold and/or interruptions is observed and maximum supportive care measures applied, a dose reduction by 250 mg is recommended. Lapatinib should not be used at doses below 1000 mg if given as monotherapy or 750 mg in combination with chemoRT. NOTE: The 750 mg dose should only be used after all supportive measures have been exhausted.

Non-hematological, grade 3 or 4 and adverse events NOT resolved to grade ≤ 2 within a maximum of 14 calendar days from last planned administration	Dose reductions by 250 mg (up to 2 reductions) will be considered after maximum supportive care recommendations are introduced.
Cardiac* *Severity corresponding to NYHA criteria; see Appendix II.	Lapatinib therapy to be discontinued permanently in the case of symptomatic NYHA class III and IV congestive heart failure OR decrease in LVEF by $> 20\%$ relative to baseline or less than the institution's lower limit of normal.

Abnormal Liver Function Tests	
In the event of grade 3 or 4 abnormal ALT and/or bilirubin, lapatinib must be discontinued permanently. Refer to Section 7.7.4.
 
For grade 1 or 2 abnormal ALT/bilirubin, lapatinib must be discontinued permanently for patients with:
 
 • BOTH bilirubin and ALT abnormalities being of grade 2 
OR
 
 • EITHER bilirubin OR ALT abnormality is grade 2 and accompanied by signs or symptoms which, in the opinion of the treating physician, are related to liver injury caused by lapatinib. 
Such signs and symptoms may include abdominal pain, fever, jaundice, rash, eosinophilia or a PS drop of ≥ 1 point from baseline. Refer to Section 7.7.4.

In case of multiple short interruptions of dose due to either adverse events or drug supply or other reasons the sum of days without lapatinib treatment should not exceed 21 days in any 90 day treatment period.
	

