7.2.2 Lapatinib/Placebo: (1/16/14)

Note: See Section 7.2.2.1 for lapatinib/placebo feeding tube administration. See Section 7.6.2 for lapatinib/placebo dose modifications.

Week 1: Starting 7 calendar days prior to radiation, patients will take 6 lapatinib/placebo tablets (1500 mg) once daily, 7 days a week, by mouth or by feeding tube on an empty stomach (either 1 hour before or 1 hour after meals). Lapatinib/placebo tablets are **not** to be crushed.

Weeks 2-7: Concurrent with radiation and cisplatin, patients will take 6 lapatinib/placebo tablets (1500 mg) once daily, 7 days a week, by mouth or by feeding tube on an empty stomach (either 1 hour before or 1 hour after meals). Lapatinib/placebo tablets are **not** to be crushed.

After Concurrent Treatment (Maintenance): After completion of radiation, patients will continue lapatinib/placebo 6 tablets (1500 mg) once daily, 7 days a week, by mouth or by feeding tube on an empty stomach (either 1 hour before or 1 hour after meals) for 3 months.

Patient Diary: Patients will be asked to document daily lapatinib/placebo on a pill diary during concurrent treatment and maintenance, which will be collected by the institution as source documentation. Institutions will submit the DP form to RTOG at the end of concurrent treatment and every month during maintenance treatment (see Sections 11.2.3 and 12.1).

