7.7 Management of Lapatinib/Placebo Adverse Events (8/5/14)

NOTE: SEE APPENDIX V FOR MANAGEMENT OF DIARRHEA.

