APPENDIX V (Continued)

Uncomplicated diarrhea is considered mild-to-moderate and defined as CTCAE v. 4 grade 1 or 2 with no complicating signs or symptoms.

Complicated diarrhea is severe and defined as any CTCAE v. 4 grade 3 or 4 diarrhea, or grade 1 or 2 with one or more of the following signs or symptoms:

- Moderate to severe abdominal cramping
- Nausea/vomiting \geq Grade2
- Decreased performance status
- Fever
- Sepsis
- Neutropenia
- Frank bleeding (red blood in stool)
- Dehydration

Management Guidelines for Patients Receiving Lapatinib Alone or as Combination Therapy

A) Uncomplicated Diarrhea

I. CTCAE Grade 1

NOTE: Patient should be instructed to start supportive care immediately at the first episode of diarrhea (i.e., unformed stool) and call their physician.

1. Administer loperamide
 - a. Initial dose 4mg followed by 2mg after every unformed stool. Re-evaluate after 24 hours, if:
 - i. Diarrhea is resolving:
 - Continue loperamide treatment at 2mg dose after every unformed stool until diarrhea free (i.e., $<$ Grade 1/bowel patterns returned to baseline) for 12 hours.
 - If diarrhea recurs, re-initiate loperamide treatment as needed to maintain normal bowel patterns
 - ii. Diarrhea is not resolving:
 - Administer loperamide at 2mg every 4 hours for the next 24 hour. Re-evaluate after 24 hours. If diarrhea is resolving, administer loperamide at 2mg after every unformed stool until diarrhea free (i.e., $<$ Grade 1/bowel patterns returned to baseline) for 12 hours. If diarrhea is not resolving continue loperamide treatment at 2mg every 4 hours and re-evaluate every 24 hours.
 - b. If Grade 1 diarrhea persists for more than 1 week with loperamide treatment, consider treatment with second-line agents (octreotide, budesonide or tincture of opium).
2. Dietary modifications which are essential in the management of diarrhea include the following recommendations (American Cancer Society; National Cancer Institute):
 - a. Stop all lactose containing products and eat small meals
 - b. Avoid spicy, fried and fatty foods, raw vegetables and other foods high in fiber
 - i. Eat foods low in fiber (i.e., lean meat, rice, skinless chicken or turkey, fish, eggs, canned or cooked skinless fruits, cooked/pureed vegetables)
 - c. Avoid caffeine and alcohol as they can irritate the bowel and increase motility
 - d. Hydration: Drink 8-10 large glasses of clear liquids a day (e.g., water, electrolyte drink).

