APPENDIX V (Continued)

- III. Persistent (≥ 3 days/72 hours) Grade 2 Diarrhea:** hold lapatinib and chemotherapy (if applicable) until diarrhea resolves ($<$ Grade 1/return to baseline bowel pattern). If supportive care measures are ineffective, consider the following:
1. If supportive care measures and the interruption of study treatment (i.e., lapatinib and if applicable chemotherapy) are ineffective in treating persistent Grade 1 or Grade 2 diarrhea, perform stool work-up, CBC, electrolytes and other tests as appropriate, consider consulting with a gastrointestinal (GI) specialist.
 - a. After diarrhea resolves (\leq Grade 1), resume treatment with lapatinib and chemotherapy (if applicable).
- IV. Recurrent Diarrhea (more than 1 occurrence of Grade 2 diarrhea):** once the 2nd occurrence of grade 2 diarrhea resolves to \leq grade 1, consider reducing the dose of lapatinib by 250mg or 1 tablet, unless the lapatinib dose already had been reduced to 750mg. No further dose reduction is recommended for patients taking lapatinib at 750mg.
1. Consider a dose reduction for chemotherapy (if applicable)

B) Complicated Diarrhea

- I. CTCAE, v 4 grade 3 or Grade 1 or 2 with complicating features (severe cramping, severe nausea/vomiting, decreased performance status, fever, sepsis, Grade 3 or 4 neutropenia, frank bleeding, dehydration)**
1. Patient **must** call physician immediately for any complicated severe diarrhea event
 2. If loperamide has not been initiated, initiate loperamide immediately: Initial dose 4mg followed by 2mg every 2 hours or after every unformed stool
 3. Refer to the dietary modification recommendations for Grade 1 and Grade 2 uncomplicated diarrhea
 4. For dehydration use intravenous fluids as appropriate, if patient presents with severe dehydration administer octreotide
 5. Perform stool work-up, CBC, electrolytes and other tests as appropriate
 6. Administer antibiotics as needed (example fluoroquinolones), especially if diarrhea is persistent beyond 24 hours or there is fever or Grade 3-4 neutropenia
 7. Hold lapatinib and chemotherapy (if applicable) until symptoms resolve to \leq Grade 1 and reintroduce lapatinib at a reduced dose (unless dose had been reduced to 750mg, contact medical monitor for further guidance)
 - a. Consider a dose reduction for chemotherapy (if applicable)
 8. Supportive care and other interventions should be continued until diarrhea free (i.e., $<$ Grade 1/bowel patterns returned to baseline) for 24 hours

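### Appendix V's diarrhea rules let lapatinib given alone fall to 750 mg, below the 1000 mg monotherapy floor in Section 7.6.2

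*Combined protocol and SAP*

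**What the plan says.** **Dose floors.** Section 7.6.2 lists the floors among its general rules for any lapatinib reduction: "Lapatinib/placebo should not be used at doses below 1000 mg if given as monotherapy or below 750 mg concomitantly with cisplatin". The grade 3-4 row of its table repeats them: "Lapatinib should not be used at doses below 1000 mg if given as monotherapy or 750 mg in combination with chemoRT". Reductions are made in 250 mg steps. For grade 1-2 non-hematologic events the table allows a single 250 mg decrease.

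**Lapatinib alone is a planned phase.** Section 7.2.2 says of maintenance: "After completion of radiation, patients will continue lapatinib/placebo 6 tablets (1500 mg) once daily", for 3 months.

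**Routing.** Section 7.2.2 says "See Section 7.6.2 for lapatinib/placebo dose modifications". Section 7.6.2 refers to Section 7.7 for managing lapatinib adverse events, and Section 7.7 opens with "SEE APPENDIX V FOR MANAGEMENT OF DIARRHEA".

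**Appendix V.** The guidelines are headed "Management Guidelines for Patients Receiving Lapatinib Alone or as Combination Therapy". Two items set a floor:
- A.IV, recurrent grade 2 diarrhea: "consider reducing the dose of lapatinib by 250mg or 1 tablet, unless the lapatinib dose already had been reduced to 750mg".
- B.I item 7, complicated diarrhea: hold the drug until symptoms are grade 1 or lower, then "reintroduce lapatinib at a reduced dose (unless dose had been reduced to 750mg, contact medical monitor for further guidance".

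**Recovery grade.** The grade 3-4 row of Section 7.6.2 holds lapatinib until grade 1 or lower, for up to 14 days. Section 7.7.1 uses grade 1, and Section 7.7.8 uses full recovery, grade 1 or baseline grade. The next row of the Section 7.6.2 table covers events that have not come down to grade 2 or lower within 14 days. Its action is that up to two 250 mg reductions will be considered.

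**The concern.** Section 7.6.2 and Appendix V both govern how far lapatinib may be reduced for diarrhea, and they give different answers when lapatinib is given alone. The main text separates monotherapy from combination and puts the monotherapy floor at 1000 mg. The appendix claims both settings and names only 750 mg. A site that follows the cross-references from Section 7.6.2 to Section 7.7 to Appendix V ends at an item that, followed as written, leads to a dose the starting section excludes.

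At stake is consistent dosing of patients with significant drug toxicity. One site could resume a maintenance patient at 750 mg, while another, applying Section 7.6.2, would not. Treatment is blinded, so the rules operate in both arms. Compliance with planned treatment is a secondary endpoint (Section 13.2) compared between arms (Section 13.6), so uneven handling could touch it slightly.

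**Working it through.** The plan states no figure to reproduce. The check is a comparison of texts plus a count of dose steps.

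**Inputs.** Full dose 1500 mg and step 250 mg (Sections 7.2.2 and 7.6.2); floors 1000 mg alone and 750 mg with cisplatin or chemoradiation (Section 7.6.2); floor 750 mg with no distinction of setting (Appendix V, A.IV and B.I item 7).

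**Dose steps.**
- 1500 − 2 × 250 = 1000 mg, the Section 7.6.2 floor for lapatinib alone.
- 1500 − 3 × 250 = 750 mg, the Appendix V floor.
- Difference: 1000 − 750 = 250 mg, one tablet; 1 − 750/1000 = 25%.

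**Side by side, by setting.**

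| Setting | Section 7.6.2 floor | Appendix V floor | Agree? |
|---|---|---|---|
| With cisplatin/chemoradiation | 750 mg | 750 mg | Yes |
| Lapatinib alone (maintenance) | 1000 mg | 750 mg | No |

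**Complicated diarrhea, maintenance patient at 1000 mg.** Under B.I item 7 the site holds the drug, waits for grade 1 or lower, and resumes at a reduced dose. The only exception is a patient already at 750 mg, and the prompt to contact the medical monitor belongs to that exception. At 1000 mg nothing stops the step: 1000 − 250 = 750 mg. Section 7.6.2 says lapatinib alone should not go there.

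**Recurrent grade 2 diarrhea, same patient.** A.IV asks the site to consider the same step, again with 750 mg as the only stop. The route differs from Section 7.6.2 in a second way. The table's grade 1-2 row permits one decrease only, to 1500 − 250 = 1250 mg from full dose, while A.IV sets no limit on the number of decreases above its floor. The count of two steps against three therefore describes the grade 3-4 and complicated-diarrhea route and not the grade 2 route.

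**Unresolved grade 3-4 events (Section 7.6.2 table), status at day 14.**
- Grade 1 or lower: the restart condition is met, so there is no problem.
- Grade 2: the restart condition is not met, yet the event has come down to grade 2 and so falls outside the unresolved row. Neither row gives an action.
- Grade 3 or higher: the unresolved row applies and says reductions will be considered, without saying that recovery must come first.

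**The case against.** **Section 7.6.2 already governs.** Its floor is one of the general rules for any lapatinib reduction, it is stated twice, and it makes no exception for diarrhea. Appendix V calls itself recommended guidance, and A.IV says only to consider a reduction. On this reading the appendix says when to reduce and Section 7.6.2 says how far. The reading is reasonable, and it is probably how a careful site would resolve the matter. But no text gives Section 7.6.2 precedence, and nothing in Appendix V limits 750 mg to combination therapy. B.I item 7 is also worded as an instruction and not as something to consider. The objection lowers the severity but does not remove the conflict.

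**The harm is small.** Affected patients must be in maintenance, already at 1000 mg, and have further qualifying diarrhea. The disputed dose is the lower one. Both points stand.

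**Stronger readings that a reader might infer:**
- *That the recovery grades contradict each other.* They do not. Grade 1 or lower is a condition for restarting; grade 2 in the next row defines when reduction is considered. The result is an ambiguity.
- *That the protocol tells sites to dose through severe toxicity.* It does not. Section 7.6.2 and Section 11.4 allow withdrawal for unacceptable adverse events, and Section 7.6.2 limits time off drug to 21 days in any 90.
- *That a patient at 750 mg when chemoradiation ends should move to 1000 mg.* The lapatinib sections contain no rule for raising a reduced dose. Writing one in would be new dosing policy, and tolerating 750 mg does not show that 1000 mg is tolerated.

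**Conclusion.** The floor conflict holds. For lapatinib given alone, Section 7.6.2 stops at 1000 mg and Appendix V at 750 mg. B.I item 7, followed as written, leads a maintenance patient at 1000 mg to a dose the main text excludes. A.IV has the same gap in softer form and also does not match the single decrease that Section 7.6.2 allows for grade 2 events. During chemoradiation the two texts agree.

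This rests on two assumptions: that maintenance counts as monotherapy, since radiation and cisplatin have ended by then, and that a reduced dose means one 250 mg step, the increment in Section 7.6.2.

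The size is one tablet a day, 25% below the monotherapy floor, in a number of patients that the documents do not give and that should be small. Nothing changes for PFS, alpha or power. The recovery-grade wording is a secondary ambiguity. Severity is minor: an internal inconsistency in an operative dosing rule that wording alone can correct.

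**What to change.** 1. **Appendix V, A.IV and B.I item 7.** Make every lapatinib reduction subject to the Section 7.6.2 floors: 1000 mg when lapatinib is given alone, 750 mg only with chemoradiation. In B.I item 7, refer a patient already at the applicable floor to the medical monitor, in place of the present trigger at 750 mg only.
2. **A.IV.** The floor alone does not settle the mismatch with the single decrease for grade 2 events. While editing the item, the sponsor should say which limit applies to recurrent grade 2 diarrhea.
3. **Section 7.6.2, row for unresolved grade 3-4 events (secondary).** State that any 250 mg reduction applies only on restart, after recovery to grade 1 or lower or to baseline grade. This also covers the event that stands at grade 2 on day 14. Leave discontinuation to the treating physician under Section 11.4, with no automatic stop at day 14.

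The cost is wording in two appendix items and one table row. It adds no patients, visits or tests, and it leaves the statistical design as it is.

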7.4.6 Lapatinib Adverse Events

7.4.6.1 Cardiac: Cardiovascular events have been seen in patients taking other compounds that inhibit ErbB2 when used in combination with or following anthracyclines, and interstitial pneumonitis has been reported in patients taking compounds that inhibit ErbB1. See Sections 7.7.1 and 7.7.2 for management guidelines.

7.4.6.2 Hepatotoxicity: Hepatobiliary events have been seen in patients taking lapatinib and other tyrosine kinase inhibitors. See Section 7.7.3 for management guidelines.

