7.7.1 Management of Non-Hematologic Adverse Events

If any of the following conditions occur, administration of lapatinib/placebo may be interrupted for a maximum of 14 days to allow the adverse event (AE) to resolve or decrease in severity:

- CTCAE, v. 4 grade 3 or 4 or unacceptable adverse events, e.g. cosmetic effect of grade 2 rash;
- No consideration and/or corroborative evidence that the AE is due to progressive disease;
- The AE is consistent with previously described lapatinib/placebo AEs. At a minimum, reassessment of AEs should be done weekly and more frequently if clinically indicated. When the AE decreases in severity to CTCAE, v. 4 grade 1, the patient may continue to take the assigned dose.

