7.7.2 Management of Asymptomatic Cardiac Adverse Events

Refer to CTCAE v. 4 grading of left ventricular cardiac function. After the baseline ECHO or MUGA, repeat LVEF assessment is required at week 12. If a patient is found to have a $\geq 20\%$ decrease in LVEF relative to baseline, or the ejection fraction is below the institution's lower limit of normal, then lapatinib/placebo should be permanently discontinued, and the patient should have a repeat evaluation of ejection fraction 28 calendar days later to confirm recovery.

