7.7.3 Management of Symptomatic Cardiac Adverse Events

Study medication must be withdrawn if a patient develops symptoms of heart failure or test results indicating abnormal LVEF (see Section 7.7.2).

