APPENDIX II

ZUBROD PERFORMANCE SCALE

- 0 Fully active, able to carry on all predisease activities without restriction**
- 1 Restricted in physically strenuous activity but ambulatory and able to carry work of a light or sedentary nature. For example, light housework, office work**
- 2 Ambulatory and capable of all self-care but unable to carry out any work activities. Up and about more than 50% of waking hours**
- 3 Capable of only limited self-care, confined to bed or chair 50% or more of waking hours**
- 4 Completely disabled. Cannot carry on self-care. Totally confined to bed**
- 5 Death**

NEW YORK HEART ASSOCIATION CLASSIFICATION OF CARDIAC DISEASE

Class	Functional Capacity	Objective Assessment
I	Patients with cardiac disease but without resulting limitations of physical activity. Ordinary physical activity does not cause undue fatigue, palpitation, dyspnea, or anginal pain.	No objective evidence of cardiovascular disease.
II	Patients with cardiac disease resulting in slight limitation of physical activity. They are comfortable at rest. Ordinary physical activity results in fatigue, palpitation, dyspnea, or anginal pain.	Objective evidence of minimal cardiovascular disease.
III	Patients with cardiac disease resulting in marked limitation of physical activity. They are comfortable at rest. Less than ordinary activity causes fatigue, palpitation, dyspnea, or anginal pain.	Objective evidence of moderately severe cardiovascular disease.
IV	Patients with cardiac disease resulting in inability to carry on any physical activity without discomfort. Symptoms of heart failure or the anginal syndrome may be present even at rest. If any physical activity is undertaken, discomfort is increased.	Objective evidence of severe cardiovascular disease.

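### The Cardiac row of the 7.6.2 dosing table gives a narrower symptomatic stop (NYHA class III-IV) than the mandatory rule in 7.7.3 (any symptoms of heart failure)

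*Combined protocol and SAP*

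**What the plan says.** **Section 7.6.2, Cardiac row.** "Lapatinib therapy to be discontinued permanently in the case of symptomatic NYHA class III and IV congestive heart failure OR decrease in LVEF by" more than 20% relative to baseline, or an LVEF under the site's lower limit of normal. Severity is by NYHA class, as set out in Appendix II. The row names no part of Section 7.7. The liver row of the same table does: "Refer to Section 7.7.4".

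**Section 7.6.2, status of the table.** The introduction says "See the table below for a summary of dose holding/interruptions and dose de-escalation recommendations" and then sends the reader to Section 7.7 in general. No text says which prevails if the two differ.

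**Section 7.6.2, general rows.** For non-hematological events of grade 1 or 2 not attributable to cisplatin or radiation, lapatinib continues at full dose with supportive care; one 250 mg reduction is allowed for prolonged grade 2 events. The grade 3-4 row requires a permanent stop for symptomatic left ventricular dysfunction of grade 3 or 4.

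**Section 7.7.2**, headed "Management of Asymptomatic Cardiac Adverse Events", calls for permanent discontinuation on an LVEF fall of 20% or more from baseline, or an LVEF under the site's lower limit.

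**Section 7.7.3.** "Study medication must be withdrawn if a patient develops symptoms of heart failure or test results indicating abnormal LVEF". It sets no NYHA threshold and gives no restart rule.

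**Section 7.4.6.1 (Cardiac).** "See Sections 7.7.1 and 7.7.2 for management guidelines". Section 7.7.3 is not cited.

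**The concern.** Sites tend to dose from the table. Here the table's symptomatic trigger starts at NYHA class III, while the rule it summarises starts at any symptoms of heart failure. For a drug given with known cardiac precautions, the quick-reference version of a safety stop should not be the laxer one.

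The usual ways of catching the difference are weak. The Cardiac row has no pointer to 7.7.2 or 7.7.3, and the cardiac cross-reference in 7.4.6.1 omits the section that holds the stricter rule. What is at stake is continued dosing of a patient with early symptomatic heart failure, against the protocol's own instruction. No endpoint, error rate or sample size is involved.

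**Working it through.** No formula applies to the main point. It rests on setting the texts side by side.

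**1. Which symptoms trigger a stop?** Appendix II describes class II as slight limitation: "Ordinary physical activity results in fatigue, palpitation, dyspnea, or anginal pain". Classes II, III and IV are therefore symptomatic, and the Cardiac row names two of those three. Section 7.7.3 has no threshold and so covers all three.

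**2. Who falls between the rules?** A patient with heart failure symptoms below class III whose LVEF has not crossed a limit, or has not been measured.

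| Patient | 7.6.2 Cardiac row | 7.7.3 |
|---|---|---|
| Class III-IV symptoms | Permanent stop | Withdraw |
| Class II, LVEF below site limit or down more than 20% | Permanent stop | Withdraw |
| Class II, no qualifying LVEF result | Not mentioned | Withdraw |

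On LVEF, the row (more than 20%) and 7.7.2 (20% or more) differ only at exactly 20%, which is marginal.

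**3. Does the rest of the table close the gap?** No. The grade 3-4 row reaches only grade 3 or 4 left ventricular dysfunction. The grade 1-2 row keeps full dose, and a site could read a mild case into it. That reading is possible, not certain: the protocol does not map NYHA class to CTCAE grade, and the specific Cardiac row may be taken to govern.

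**4. Do other sections close it?** Section 7.7.8 calls for interruption of up to 14 days for clinically significant lower-grade events, so a site that missed 7.7.3 still has grounds for a hold. That is weaker than 7.7.3, because drug may then be resumed. Section 7.7.1 likewise says drug "may be interrupted for a maximum of 14 days".

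**5. Would LVEF monitoring catch these patients?** Only in part. Planned dosing is 1 week lead-in + 6 weeks with radiotherapy + about 13 weeks (3 months) maintenance = about 20 weeks. One post-baseline LVEF is scheduled, at week 12, which 11.2.1 also describes as 4 weeks after radiotherapy (7 + 4 = week 11). That leaves 11-12 weeks before it and 8-9 weeks after it (20 - 12 = 8; 20 - 11 = 9) with none scheduled. This explains why symptoms matter as a trigger; it does not measure how many patients are affected.

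**6. Cross-references from 7.4.6 to 7.7.**

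| Subsection | Cites | Topic is in |
|---|---|---|
| 7.4.6.1 Cardiac | 7.7.1, 7.7.2 | 7.7.2, 7.7.3 |
| 7.4.6.2 Hepatotoxicity | 7.7.3 | 7.7.4 |
| 7.4.6.3 Dermatologic | 7.7.4 | 7.7.5 |
| 7.4.6.4 Nausea/vomiting | 7.7.5 | 7.7.6 |
| 7.4.6.5 Interstitial lung disease | 7.7.6 | 7.7.7 |

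All five are shifted by one, but only the first bears on this point, and it does reach one correct cardiac section, 7.7.2.

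**The case against.** The strongest reply is that the protocol already signals which text to follow. The table calls itself a summary of recommendations and defers to 7.7, where 7.7.3 says must. A site that kept such a patient on drug would be in breach. This stands, and it rules out two stronger readings that a reader might infer: that the protocol has no stop for mild symptomatic heart failure, and that the row instructs sites to continue. The row is silent on these patients; the stop exists in 7.7.3.

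Several backstops are also real. A history of heart failure or of LVEF under 50% is excluded (3.2.13.3). History and physical are weekly during radiotherapy (11.2.5), though afterwards 11.2.6 lists visits at 4 weeks and 3 months while maintenance continues. Section 7.7.8 supports a hold, and 11.4 lets the physician stop for unacceptable events. A reader sent to 7.7.2 lands directly above 7.7.3.

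Two points of interpretation also count. Section 7.7.3 says withdrawn, not permanently discontinued, so it cannot be assumed to demand a permanent stop. And class II symptoms include fatigue, which 6.9 lists as a common radiation effect, so an unqualified any-symptom rule could be triggered by non-cardiac complaints.

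Finally, little dosing may remain. Section 7.9 is dated March 2017, accrual was projected to finish around then (13.5), and concurrent therapy around July 2017 (13.6.3). With 3 months of maintenance, dosing would run to about October 2017. That limits the benefit of an amendment but does not remove the inconsistency.

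**Conclusion.** The inconsistency holds in a limited form. The symptomatic trigger in the Cardiac row is a strict subset of the one in 7.7.3. The difference is milder symptomatic heart failure, such as class II, without a qualifying LVEF result. For those patients the table gives no stop and could be read as full-dose continuation, while 7.7.3 requires withdrawal.

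No patient count can be given; the group is probably small. The conclusion assumes that symptoms of heart failure in 7.7.3 include class II symptoms. That follows from Appendix II, although 7.7.3 names no class.

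A reader might take the run of five shifted references as evidence of a wider failure of the safety rules. The documents do not support that. Four are clerical and unrelated to the cardiac rule, and the liver references inside 7.6.2 are correct. There is no effect on sample size, alpha, power or the interpretation of PFS. The correction should be made because it concerns patient safety and the protocol's own mandatory rule already supports it.

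**What to change.** 1. Reword the 7.6.2 Cardiac row in two parts. Study drug must be withdrawn for any symptoms of heart failure that the investigator attributes to cardiac dysfunction (per 7.7.3). It is permanently discontinued for symptomatic NYHA class III-IV failure, an LVEF fall of 20% or more from baseline, or an LVEF under the site's lower limit of normal (per 7.7.2). The attribution wording keeps radiation fatigue from triggering the rule.
2. State in 7.7.3 whether withdrawal is permanent and, if not, the conditions for restart.
3. Add a pointer to 7.7.2 and 7.7.3 in the row. State that heart failure and LVEF events follow those sections, not the grade 1-2 row or the 7.7.1 hold-and-restart rule. Limit the statement to those events, because 7.7.2 and 7.7.3 do not cover other cardiac events.
4. Correct 7.4.6.1 to cite 7.7.2 and 7.7.3, and fix the clerical slips in 7.4.6.2 to 7.4.6.5 in the same amendment.

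The cost is amendment wording. The downside is that a few patients with mild symptoms, whom a site might have continued under the table, would stop drug.
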